8.3 Statistical Analysis Plan

8.3.1 Efficacy Endpoints for Grade III-IV and Grade II GVHD.

The statistical test used for endpoints (Z test of proportions) takes the currently available 3 year JTCC data as the historical control data set for comparison. In reviewing these data, as currently available, it appears that the JTCC rates of severe GVHD, NRM, and cancer relapse are somewhat lower (i.e. better patient outcomes) than the national averages from published studies. For our final determinations of significance, we will use updated JTCC 3 year data as they become available at time of study completion.

Outcome variables examined include engraftment, GVHD, relapse, and NRM, however the efficacy hypotheses are constructed in relation to GVHD only.

Primary endpoint analysis

Historic GVHD data are available on 178 allogeneic transplants, of whom 46 (26%) experienced grade III or IV acute GVHD. All the other allogeneic transplantees (74%) had grade II GVHD. Based on these data, if 8 or fewer of the total 60 study participants experience grade III - IV acute GVHD during the course of the study, we will have demonstrated a protective effect for this criterion, with a $p < 0.05$, based on a one-way Z test for a decreased proportion.

Sample Size and Power Calculation Considerations

If we use the proportion $P=0.26$ as the rate of Grade III - IV GVHD in the current standard treatment, then using a one-sided exact test of the proportion and significance level of 0.05, testing if 9/60 (15%) rate of Grade III-IV GVHD is achievable with telmisartan treatment will have 58.8% power to detect this effect, if it exists. Testing for a 12% rate would achieve 82.2% power. Using the recommended level of significance, 0.025, for a one-sided test, testing if the grade III-IV GVHD by day 100 is 0.15, would have power of 44.4% of detecting this effect. At the 2.5 % level, testing if the rate is less than 0.11, will have 79.0 % power of detecting. Testing if the rate of grade III-IV in telmisartan treated transplantees is 0.10, will have 85.8% power of detecting this effect using the 2.5 % level of significance.

Numeric Results for testing $H_0: P = P_0$ versus $H_1: P < P_0$ using the PASS13 sample size software Test Statistic: Exact Test

Power	N	Proportion		Target Alpha	Actual Alpha	Beta	Reject H_0 If $R \leq$ This
		Given H_0 (P_0)	Given H_1 (P_1)				
0.8584	60	0.2600	0.1000	0.0250	0.0140	0.1416	8
0.7899	60	0.2600	0.1100	0.0250	0.0140	0.2101	8

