Incidence of Grade II GVHD

The historical data reported a rate of incidence of 74%. At 5% level of significance, a one-sided exact test of whether telmisartan can attain lower levels of 62% (37/60), would achieve 63.2 % power of detecting this if it is indeed efficacious. A lower incidence rate of 60% will be detected with 74.5% power.

Using the recommended level of significance, 0.025, a one-sided exact test of whether Telmisartan can attain the lower incidence rate of 62% will achieve a power of 52.8% to detect this effect. A one-sided exact test of whether the grade II GVHD incidence rate of 0.50 (30/60) can be attained by Telmisartan will have 97.4% power to detect this effect. A one-sided exact test of whether the incidence rate of 60% is possible with telmisartan will achieve power of 65.1% to detect it. A one-sided exact test of whether the grade II GVHD incidence rate of 0.57 can be attained by Telmisartan will have 80.5% power to detect this effect.

Numeric Results for testing $H_0: P = P_0$ versus $H_1: P < P_0$ using the PASS13 sample size software Test Statistic: Exact Test

Power	N	Proportion Given H0 (P0)	Proportion Given H1 (P1)	Target Alpha	Actual Alpha	Beta	Reject H0 if $R \leq$ This
0.9741	60	0.7400	0.5000	0.0250	0.0242	0.0259	37
0.8448	60	0.7400	0.5600	0.0250	0.0242	0.1552	37
0.8047	60	0.7400	0.5700	0.0250	0.0242	0.1953	37
0.7587	60	0.7400	0.5800	0.0250	0.0242	0.2413	37
0.6507	60	0.7400	0.6000	0.0250	0.0242	0.3493	37
0.5904	60	0.7400	0.6100	0.0250	0.0242	0.4096	37
0.5275	60	0.7400	0.6200	0.0250	0.0242	0.4725	37

Thus, with respect to grade 2 acute GVHD, if 37 or fewer patients of the 60 have grade 2 or lower acute GVHD, we will have demonstrated a drug effect at $p < 0.05$, using the one-way Z test of proportions.

To summarize, with only 26% of JTCC patients during the past 3 years exhibiting grade III or IV acute GVHD, we would have to see no more than 7 cases of grade III or IV acute GVHD (~ 12%) by the completion of the study to conclude that severe aGVHD had been reduced. However, with 74% of JTCC patients experiencing grade II aGVHD, we need only reduce that to 60%, or 36 of 60 patients having no more than grade II acute GVHD, in order to achieve significance.

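### All stated power treats the estimated centre control rate as known, while the final Z test is not identified as one- or two-sample and its updated control cohort has no fixed selection rule

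*Combined protocol and SAP*

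**What the plan says.** Section 8.3.1 names a Z test of proportions that "takes the currently available 3 year JTCC data as the historical control data set for comparison". It then says: "For our final determinations of significance, we will use updated JTCC 3 year data as they become available at time of study completion". Under Primary endpoint analysis it states: "Historic GVHD data are available on 178 allogeneic transplants", 46 of them (26%) with grade III-IV disease. The remaining 74% are taken as grade II.

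The success rule for grade III-IV is met "if 8 or fewer of the total 60 study participants experience grade III - IV acute GVHD during the course of the study". For grade II, "if 37 or fewer patients of the 60 have grade 2 or lower acute GVHD, we will have demonstrated a drug effect". The closing summary of 8.3.1 gives different counts: "we would have to see no more than 7 cases of grade III or IV acute GVHD", and 36 rather than 37 for grade II.

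The power section takes 0.26 "as the rate of Grade III - IV GVHD in the current standard treatment, then using a one-sided exact test of the proportion". Both PASS tables are one-sample, with the null proportion fixed at 0.26 or 0.74 and a target alpha of 0.025. The text also gives powers at 0.05.

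On timing, part of the power text refers to day 100 ("testing if the grade III-IV GVHD by day 100 is 0.15"), whereas the success rule counts cases over the whole study. Section 5.1 follows patients to Day +180. Section 8.4 uses 26% as the expected registry rate for its day-100 rule on grade 3 or 4 GVHD, although the text there mislabels the event as NRM.

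**The concern.** All subjects receive open-label telmisartan, so the centre rate is the whole comparator. Two things about it are loose.

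First, the power calculation and the final test do not match. Power assumes the control rate is known without error. The final test compares with a rate estimated from a finite cohort, and the plan does not say whether that cohort's sampling error enters the test. If it does, power is lower than stated. If it does not, the false-positive rate is higher than nominal.

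Second, the reference is settled only at study completion, when open-label outcomes are known. The centre, the three-year length and the rough timing are given. The data cut-off, calendar dates, an eligibility filter and a rule on trial participants are not. Section 4.1.1 requires, for example, a 7/8 or 8/8 HLA match, Karnofsky of at least 70 and a comorbidity score below 5. Section 5.5.2 counts only patients still on drug at Day +14 as evaluable. Nothing says the 178 met comparable conditions. The same trial result could pass or fail depending on which records enter the updated set.

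**Working it through.** **Inputs (8.3.1):** trial N = 60; control 46/178 for grade III-IV; 74%, i.e. 132/178, for grade II; one-sided alpha 0.025 or 0.05.

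**1. Reproduce the plan (control rate fixed).** With X ~ Bin(60, p):
- Grade III-IV: P(X ≤ 8 | 0.26) = 0.0140; P(X ≤ 8 | 0.10) = 0.8584; P(X ≤ 8 | 0.11) = 0.7899; P(X ≤ 8 | 0.15) = 0.445 (plan: 44.4%).
- Grade II: P(X ≤ 37 | 0.74) = 0.0242; P(X ≤ 37 | 0.57) = 0.8047.

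The stated figures are therefore correct for the test they describe.

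**2. Precision of the control.** 46/178 = 25.8%, with an exact 95% CI of 19.6% to 32.9%.

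**3. Reading (a): two-sample Z.** Let Y ~ Bin(178, p0) and p̄ = (X + Y)/238. Then Z = (Y/178 − X/60) / √[p̄(1 − p̄)(1/60 + 1/178)], and the test rejects when Z ≥ 1.96 (0.025) or 1.645 (0.05). Rejection probabilities are summed exactly over all (X, Y).

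**4. Reading (b): one-sample Z with the observed rate plugged in.** Z = (Y/178 − X/60) / √[(Y/178)(1 − Y/178)/60], summed in the same way.

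Results at nominal one-sided 0.025:

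| Quantity | Stated | (a) two-sample Z | (b) plug-in Z |
|---|---|---|---|
| Type I error, grade III-IV (26%) | 0.0140 | 0.022 | 0.038 |
| Type I error, grade II (74%) | 0.0242 | 0.028 | 0.054 |
| Power, grade III-IV at 10% | 85.8% | 78.7% | 84.7% |
| Power, grade III-IV at 11% | 79.0% | 71.8% | 78.8% |
| Power, grade III-IV at 15% | 44.4% | 41.3% | 50.3% |
| Power, grade II at 57% | 80.5% | 68.9% | 78.9% |
| Power, grade II at 60% | 65.1% | 53.6% | 65.5% |

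A plug-in exact test lies between these for type I error (0.032 and 0.039). Its power is 83.1% at 10%, 76.9% at 11% and 47.6% at 15% for grade III-IV, and 74.2% at 57% for grade II.

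**5. Sensitivity to the updated set, assuming its size stays at 178.** For 8/60 by two-sample Z:
- Against 42/178: p̄ = 50/238 = 0.210; difference 0.2360 − 0.1333 = 0.1026; SE 0.0608; Z = 1.69; p = 0.046.
- Against 41/178: p̄ = 49/238 = 0.206; difference 0.0970; SE 0.0604; Z = 1.61; p = 0.054.
- At 0.025 the margin is one control patient: 46/178 gives p = 0.023 and 45/178 gives p = 0.027.

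If all 178 were new, independent patients at an unchanged true 26% (an assumption), P(Y ≤ 41) = 0.21. Records carried over from the current set would lower this.

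**6. What survives with the current 178 at one-sided 0.05, two-sample.**
- 8/60 against 46/178 gives p = 0.023; 37/60 against 132/178 gives p = 0.033.
- The 0.8 power claims in section 8.2: a 62% reduction gives 0.26 × 0.38 = 9.9%, power 88%; a 25% reduction gives 0.74 × 0.75 = 55.5%, power 84%.
- At 0.025 the same two powers are 79.5% and 75.7%, and 37/60, the cut-off printed in the 0.025 table, no longer passes.

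**The case against.** The strongest reply has four parts.

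*The update is declared in advance.* Centre, length and timing are fixed, and a rolling three-year set ending at completion is more contemporary than the current one. This stands. Making the updated cohort primary is legitimate; what is missing is its selection rule. The 42-versus-41 comparison shows that any threshold has an edge. It matters here only because nothing settles which records count.

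*The conclusions hold anyway.* At one-sided 0.05, the level 8.3.1 attaches to the rules of 8 and 37, they do, as step 6 shows. But the PASS tables use 0.025, and the plan says the current 178 will not be the final comparator.

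*This is a pilot, where a fixed null rate is a common simplification.* True, but 8.3.1 still sets formal counts for having demonstrated an effect.

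*The historical window is not really open.* Section 8.4 ties the 26% to day 100. This stands in part: day 100 is implied for the control, though not formally defined. The mismatch is on the trial side, where cases are counted over the whole study.

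Three stronger inferences are tempting and not supported. A reader might conclude that power is overstated whichever test is meant; under plug-in it changes little and exceeds the stated value at some alternatives, such as 50.3% against 44.4% at 15%. A reader might add inflated type I error to lost power; they belong to different tests. A reader might suppose that trial participants will enter the updated control. Section 4.2.1 offers the trial to every eligible patient, so overlap is possible, but calling the set historical suggests otherwise and no rule says either way. If participants with fewer cases were included, they would lower the control rate and make the test conservative.

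**Conclusion.** The point holds, and the plan should be changed. Whichever way the Z test is read, a stated property fails. As a two-sample test, power at 0.025 is about 7 points below the stated value for grade III-IV at 10% and 11%, and about 12 points below for grade II at 57%. As a plug-in one-sample Z test, type I error at nominal 0.025 rises to 0.038 for grade III-IV and 0.054 for grade II.

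The absence of a fixed selection rule for the updated cohort is a separate weakness. It can decide a borderline result, but the documents give no sign that it would be used that way.

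The figures assume true control rates of 26% and 74%, a control of 178 and binomial sampling. The grade II figures also depend on the 74%, which is simply everyone without grade III-IV disease. Its derivation is a separate doubt that this point does not resolve.

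**What to change.** In section 8.3.1:

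1. Name a two-sample test of the 60 against the control cohort.
2. Before outcomes are analysed, fix the control's selection rule: calendar dates or an explicit update rule, data cut-off and the trial's eligibility criteria. Exclude all trial participants.
3. Either the current or the updated cohort may be primary if its rule is fixed in advance. Use the other as a sensitivity analysis for change over time.
4. Count GVHD to day 100 in both groups for this comparison.
5. Choose one alpha, and restate power and a single cut-off per endpoint from the final eligible cohort. With the unfiltered 178 the two-sample cut-offs would be 8 and 36 at 0.025, or 9 and 37 at 0.05. These are illustrations and would change with filtering.

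The cost is SAP wording and a registry query. Quoted power falls as shown above, and further if filtering shrinks the control. With 120 controls left (assumed), power at 0.025 would be 75.0% for grade III-IV at 10% and 63.7% for grade II at 57%. At 0.05 it would be 84.7% and 74.4%. If the earlier cohort is made primary, the comparison is less contemporary, hence the sensitivity analysis.

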5.5.2 Replacement of Subjects

The study will enroll a total of 60 evaluable subject defined as subjects who remain on telmisartan treatment through Day + 14 post-HCT. Patients who discontinue telmisartan **before** day +14 post-HCT will be replaced by an additional subjects until a total of 60 evaluable subjects is reached. However, for safety reasons, we will continue to follow their medical progress for up to 180 days post-transplant. Those who discontinue telmisartan **after** day + 14 post-HCT will not be replaced and will be continued to be followed through the 180 day study period. Subjects who discontinue telmisartan at any time will continue all other study assessments and time points unless they choose to discontinue the study.

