8.2 Sample Size

Enrollment of 60 subjects for this pilot study is based on the available patient population undergoing allogeneic HCT at the John Theurer Cancer Center (JTCC), expected rates of enrollment, and the historical data set from the past 3 years' allogeneic HCT experience at the JTCC, as well as the published literature from many centers performing allogeneic HCT for the same underlying diseases, and using similar preparative regimens. Statistical power of 60 subjects was considered adequate to detect fairly dramatic reductions of GVHD, as described in the Statistical Plan, below. Reductions of ~ 25% in grade II GVHD, and of ~ 62% in grade III-IV GVHD should be detected with 0.8 power, as discussed below. The similarly designed Maraviroc study [17] enrolled 38 patients, and reached statistical significance due to almost complete elimination of Grade III-IV GvHD. As we do not anticipate equally strong suppression of GVHD with telmisartan, we estimated that the somewhat larger number of 60 subjects would be appropriate to detect 60 -70% reduction. However, even a 20- 30% decrease in severe GVHD would have a real impact in the clinic, and this pilot study is not powered to detect this. Since grade II GVHD is more common, we are powered to detect a roughly 25% reduction in its

occurrence. This would be clinically beneficial, and would support further study of telmisartan for this indication.

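### Section 8.3.1 gives 82.2% power for a 12% grade III-IV GVHD rate, but its decision rule of 8 or fewer cases has 71.0%: the 5%-level powers belong to cut-offs that the plan never adopts

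*Combined protocol and SAP*

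**What the plan says.** All of this is in the combined protocol and SAP.

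- **Decision rule, grade III-IV (8.3.1, primary endpoint analysis).** A protective effect is shown "if 8 or fewer of the total 60 study participants experience grade III - IV acute GVHD", at p<0.05, "based on a one-way Z test for a decreased proportion".
- **Power at the 5% level (8.3.1).** The null rate is 26%, and the calculation is made "using a one-sided exact test of the proportion and significance level of 0.05". It gives 58.8% at a true rate of 15%, and then: "Testing for a 12% rate would achieve 82.2% power". No cut-off accompanies these figures. The count 9/60 appears only as the arithmetic form of the 15% alternative.
- **Power at the 2.5% level (8.3.1).** The plan calls this level the recommended one. It gives 44.4% at 15%, 79.0% at 11% and 85.8% at 10%. The PASS table gives the cut-off as 8 or fewer, with actual alpha 0.0140.
- **Grade II (8.3.1).** The null rate is 74%. At 5% the power is 63.2% for a rate of 62%, and "A lower incidence rate of 60% will be detected with 74.5% power". At 2.5% the text and table give 52.8% at 62% and 65.1% at 60%, with a cut-off of 37 or fewer. The decision sentence uses 37 and labels it p<0.05 by a Z test.
- **Closing summary (8.3.1).** It gives other counts: no more than 7 cases for grade III-IV, and 36 of 60 for grade II.
- **Sample size (8.2).** "Reductions of ~ 25% in grade II GVHD, and of ~ 62% in grade III-IV GVHD should be detected with 0.8 power".

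**The concern.** Both decision sentences carry a p<0.05 label, so a reader will pair them with the powers quoted at the 5% level. Those powers come from a more lenient test than the one that the printed counts apply. Two things are at stake. First, a reader would take the trial to have over 80% power against a true grade III-IV rate of 12%, which is also the rate that the closing summary attaches to its limit of 7 cases. Second, the level (0.05 or 0.025), the test (exact or Z) and the count are not tied together. A borderline result could therefore be called positive or negative depending on which sentence is followed.

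**Working it through.** **Inputs.** n = 60 (5.5.2: "The study will enroll a total of 60 evaluable subject"). Null rates are 0.26 for grade III-IV and 0.74 for grade II (8.3.1). The historical counts are 46/178 for grade III-IV (8.3.1) and, by subtraction, 132/178 for grade II.

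**Step 1: reproduce the plan's powers.** The exact lower tail is P(X ≤ r) = Σ C(60,k) p^k (1−p)^(60−k) for k = 0 to r. The cut-off r is the largest count whose tail at the null rate does not exceed alpha.

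Grade III-IV:

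| Reject if | Size at 26% | Power at 15% | Power at 12% | Power at 11% | Power at 10% |
|---|---|---|---|---|---|
| ≤7 | 0.0055 | 30.5% | 56.7% | 66.2% | 75.2% |
| ≤8 | 0.0140 | 44.5% | **71.0%** | 79.0% | 85.8% |
| ≤9 | 0.0312 | 58.8% | **82.2%** | 88.1% | 92.7% |
| ≤10 | 0.0620 | 71.6% | 90.1% | 93.9% | 96.6% |

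Grade II:

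| Reject if | Size at 74% | Power at 62% | Power at 60% |
|---|---|---|---|
| ≤36 | 0.0124 | 42.2% | 54.9% |
| ≤37 | 0.0242 | 52.8% | 65.1% |
| ≤38 | 0.0447 | 63.2% | 74.3% |
| ≤39 | 0.0776 | 72.7% | 82.1% |

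At 5% the exact cut-offs are ≤9 and ≤38, and the four 5%-level powers reproduce there (74.3% against a printed 74.5% is trivial). At 2.5% the cut-offs are ≤8 and ≤37, as in the PASS tables, and the plan's 2.5%-level figures reproduce as well.

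**Step 2: match each 5%-level power to the printed rule.**

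| Scenario | Printed at 5% | Under ≤8 or ≤37 | Difference (points) | Lower figure printed in the plan? |
|---|---|---|---|---|
| III-IV, 15% | 58.8% | 44.5% | 14.3 | Yes, 44.4% |
| III-IV, 12% | 82.2% | 71.0% | 11.2 | **No** |
| II, 62% | 63.2% | 52.8% | 10.4 | Yes, 52.8% |
| II, 60% | 74.5% | 65.1% | 9.4 | Yes, 65.1% |

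**Step 3: 9 or 10 grade III-IV cases under the candidate tests (one-sided p).**

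- One-sample Z: z = (x/60 − 0.26)/√(0.26×0.74/60), with standard error 0.0566. For x = 9, z = −0.110/0.0566 = −1.94.
- Two-sample Z against 46/178: for x = 9 the pooled rate is 55/238 = 0.231, the standard error is √(0.231×0.769×(1/60+1/178)) = 0.0629, and z = (0.150 − 0.258)/0.0629 = −1.72. The continuity correction moves the difference towards zero by ½(1/60+1/178) = 0.0111, giving z = −1.55.

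| Test | 9 cases | 10 cases |
|---|---|---|
| Exact binomial | 0.031 | 0.062 |
| One-sample Z, uncorrected | 0.026 | 0.0497 |
| One-sample Z, corrected | 0.036 | 0.067 |
| Two-sample Z, uncorrected | 0.042 | 0.074 |
| Two-sample Z, corrected | 0.061 | 0.101 |

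**Step 4: Section 8.2.** A 62% reduction is 0.26 × 0.38 = 0.099, or about 10%. A 25% reduction is 0.74 × 0.75 = 0.555. Under ≤8 and ≤37 the powers there are 85.8% (at 10%) and about 86%, both above 0.8. Under the summary's ≤7 and 36/60 they are 75.2% and 79.7%, both below 0.8.

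**The case against.** The strongest reply is that nothing is miscalculated. Each 5%-level power is labelled with its level and with the exact test, and each reproduces. The plan shows power at two levels and, for three of the four scenarios, prints the lower value shortly afterwards. A reader might infer that the trial generally has up to 14 points less power than the plan states. The documents do not support that: the 14-point gap is 58.8% against 44.4%, and both numbers are on the page. This part of the reply stands, and it confines the missing figure to the 12% rate.

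A reader might also infer that the p<0.05 label is false, or that 9 and 10 cases would both be significant under the named test. Neither follows. Eight and 37 cases do give p<0.05 under every Z variant (corrected two-sample: 0.034 and 0.047). The plan describes its Z test as using the historical data set as control, which reads naturally as a two-sample comparison. With a continuity correction, that test has exactly 8 and 37 as its 5% cut-offs. This is an admissible reading, but the plan specifies no correction, and its tables derive the same counts from an exact 2.5% test. Ten cases is significant only by the uncorrected one-sample Z.

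Finally, a reader might infer that the headline power in Section 8.2 is wrong. Under ≤8 and ≤37 it is conservative.

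The reply leaves one point unanswered. The only power printed for a 12% rate is not the power of any decision rule in the plan.

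**Conclusion.** The concern holds in a limited form. At a 12% grade III-IV rate the plan prints 82.2%, while its rule of 8 or fewer gives 71.0%, a gap of 11.2 points; the summary's limit of 7 gives 56.7%. The other 5%-level powers are correct for cut-offs of 9 and 38, but those cut-offs are not decision rules, and the shared p<0.05 label invites the wrong pairing. A result of 9 cases fails the printed rule, although it is significant at 0.05 by every test in Step 3 except the corrected two-sample Z.

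These results assume 60 evaluable patients and null rates fixed at 0.26 and 0.74. The unrounded 46/178 leaves the exact cut-offs unchanged (size 0.0150 for ≤8, 0.0331 for ≤9). The plan intends to use updated historical data for the final determination of significance, and that could move the null rates.

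**What to change.** Name one test, one level and one cut-off per endpoint for the decision. The simplest choice is the exact one-sided 2.5% test already tabulated: 8 or fewer for grade III-IV, and 37 or fewer for grade II. Then:

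- make the Z-test and p<0.05 wording in both decision sentences agree with that choice, and bring the summary's 7 and 36 into line;
- delete the 5%-level powers, or mark them clearly as not applying to the decision rule;
- state the grade III-IV power for the rule of 8 or fewer as 85.8% at 10%, 79.0% at 11%, 71.0% at 12% and 44.5% at 15%.

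Section 8.2 needs no change under 8 and 37. If the summary's 7 and 36 were kept instead, its 0.8 power would have to be restated (75.2% at a 10% rate, 79.7% at 55.5%).

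The cost is SAP wording, with no change to sample size or conduct. Replacing the named Z test by the exact test is a real choice and should be recorded as one. A result of 9 cases could then not be claimed as significant, and the stated power at 12% falls from 82.2% to 71.0%.

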3.0 STUDY OBJECTIVES

3.1 Primary Objective

To assess the utility of adding telmisartan at 160 mg/day (or the highest tolerated dose of 40, 80, or 160 mg, daily) to standard GvHD prophylaxis for the prevention of grade II or greater acute graft vs. host disease (aGVHD) in patients receiving allogeneic HCT.

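### Section 8.3.1 leaves the efficacy decision rule open: two significance levels, two kinds of test, two pairs of cut-offs, and no ranking of the two GVHD endpoints

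*Combined protocol and SAP*

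**What the plan says.** All references are to the combined protocol and SAP.

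- **Objective (3.1).** The aim is stated "for the prevention of grade II or greater acute graft vs. host disease (aGVHD) in patients receiving allogeneic HCT".
- **Null rates (8.3.1).** "Historic GVHD data are available on 178 allogeneic transplants, of whom 46 (26%) experienced grade III or IV acute GVHD". All remaining historical patients (74%) are said to have had grade II, so the two categories add to 100%.
- **Grade III-IV rule (8.3.1, under the primary endpoint heading).** With 8 or fewer cases among 60, "we will have demonstrated a protective effect for this criterion, with a" p below 0.05, "based on a one-way Z test for a decreased proportion".
- **Grade II rule (8.3.1).** "if 37 or fewer patients of the 60 have grade 2 or lower acute GVHD, we will have demonstrated a drug effect at" p below 0.05, again by a one-sided Z test.
- **Levels used for power (8.3.1).** First "using a one-sided exact test of the proportion and significance level of 0.05", then "Using the recommended level of significance, 0.025, for a one-sided test, testing if the grade III-IV GVHD by day 100 is 0.15". The two printed PASS tables are exact tests at 0.025, with rejection at 8 or fewer and at 37 or fewer.
- **Closing summary (8.3.1).** The counts become 7 for grade III-IV and 36 for grade II.
- **Control data (8.3.1).** Final significance is to use three-year centre data updated at study completion.

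Nothing ranks the two GVHD tests, makes one conditional on the other, or splits alpha between them. Multiplicity is addressed elsewhere: a Bonferroni cut-off for the exploratory Shannon index (8.3.2) and a joint error for the five stopping rules (8.4).

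**The concern.** A decision rule needs one level, one test, one cut-off and one deciding endpoint. Section 8.3.1 offers alternatives for each, and they disagree at counts the trial could plausibly produce. With 9 severe cases, one sentence of the plan is satisfied (p<0.05) and another is not (8 or fewer). With 8, the rule is met but the summary is not. Because the control data will be updated, the printed counts need not be the ones finally applied, so the p-value label could decide.

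The two stand-alone rules raise a second question: how often would a drug with no effect be declared effective by at least one of them? The plan gives no such figure, and the answer depends on which of its versions is used.

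**Working it through.** **Inputs.** N = 60; null rates 0.26 (46/178) and 0.74; cut-offs 8/37 and 7/36 (all 8.3.1); Table 13 boundary (8.4).

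**1. The plan's own figures.** Exact lower tail P(X ≤ r | 60, p):

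- P(X ≤ 8 | 0.26) = 0.0140 and P(X ≤ 37 | 0.74) = 0.0242, the printed actual alphas.
- P(X ≤ 8 | 0.10) = 0.8584 and P(X ≤ 37 | 0.57) = 0.8047, the printed powers.
- The powers quoted at level 0.05 use different cut-offs. P(X ≤ 9 | 0.15) = 58.8%, P(X ≤ 9 | 0.12) = 82.2% and P(X ≤ 38 | 0.62) = 63.2% all match.

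**2. Which level each cut-off belongs to (exact test).**

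| One-sided level per test | Grade III-IV cut-off (alpha) | Grade II cut-off (alpha) |
|---|---|---|
| 0.0125 | 7 (0.0055) | 36 (0.0124) |
| 0.025 | 8 (0.0140) | 37 (0.0242) |
| 0.05 | 9 (0.0312) | 38 (0.0447) |

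So 8/37 are 0.025 cut-offs carrying a p<0.05 label. The summary pair 7/36 matches 0.0125 per test, but the plan does not say that a split was intended.

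**3. Nine and ten severe cases.**

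- Nine, exact: 0.031.
- Nine, one-sample Z: (0.15 − 0.26)/√(0.26 × 0.74/60) = −0.11/0.0566 = −1.94, p = 0.026.
- Nine, two-sample Z against 46/178: pooled rate 55/238 = 0.231; z = (0.150 − 0.258)/0.0629 = −1.72, p = 0.042.
- Ten: exact 0.062, one-sample Z 0.0497, two-sample Z 0.074.

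Nine meets p<0.05 by all three tests and fails the printed count. Ten meets it by one test only.

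**4. Chance of at least one false claim, ignoring the stopping rules.** With a 26%/74% split that covers every patient, grade II in 37 or fewer means grade III-IV in 60 − 37 = 23 or more. That cannot occur together with 8 or fewer, so the two errors add.

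| Rule | Sum | Result |
|---|---|---|
| 7/36 (summary) | 0.0055 + 0.0124 | 0.018 |
| 8/37 (decision sentences) | 0.0140 + 0.0242 | 0.038 |
| 9/38 (exact, 0.05 each) | 0.0312 + 0.0447 | 0.076 |
| 10/38 (one-sample Z, 0.05 each) | 0.0620 + 0.0447 | 0.107 |

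**5. The same with Table 13 applied.** Table 13 stops the trial at 20 severe cases among 59 patients or 21 among 60. Applying it patient by patient gives stopping probabilities of 0.247 at a 26% rate and 0.790 at 36%, as Table 14 prints. A trial that finishes unstopped has at most 20 severe cases, hence at least 40 grade II cases. Grade II counts of 36, 37 or 38 need 24, 23 or 22 severe cases and cannot be reached. What remains is the grade III-IV error alone: 0.014 at cut-off 8, 0.031 at 9 and 0.062 at 10.

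**6. Direction of the grade II rule.** Under the same split, the grade II count falls when severe GVHD rises. If the true grade III-IV rate were 36%, which section 8.4 calls unacceptable, P(X ≤ 37 | 0.64) = 0.40 before stopping is considered.

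**The case against.** The tempting stronger reading is that two unadjusted tests push the false-claim rate above the stated level. A reader might infer this from the absence of any hierarchy, but the documents do not support it as a general statement. The decision sentences state p<0.05 with cut-offs 8/37, whose combined error of 0.038 is below 0.05. The summary pair gives 0.018, below both levels. Once Table 13 is applied, the grade II route adds essentially nothing. The only figure still above 0.05 is 0.062 at cut-off 10, and that comes from the one-sample Z approximation, not from having two tests.

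A reader might also infer that the level can be picked after the data are seen. That too goes beyond the text: counts are printed, both decision sentences use p<0.05, and 0.025 appears only in the power material. Nowhere does the plan declare success at 9 or 10 cases.

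The setting is a further defence. This is a pilot, section 8.2 says a grade II reduction would support further study, section 11.7 disclaims a labelling purpose, and each rule is worded for its own criterion. Strict family-wise control is therefore less pressing than in a confirmatory trial.

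These arguments limit the size of the error. They do not remove the conflict in the threshold: the section speaks of having demonstrated an effect, and 8 or 9 severe cases would still be read differently depending on the sentence used. Nor does the primary endpoint heading over grade III-IV settle the ranking, because section 3.1 names grade II or greater and section 2.0 lists several primary endpoints.

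**Conclusion.** The point holds as an unfixed decision rule. Level, test, cut-off and deciding endpoint each appear in versions that disagree, and the disagreement bites at 8 and 9 severe cases. The inflation is modest and conditional: without stopping, 0.038 for 8/37 exceeds 0.025 but not 0.05, and 0.05 is exceeded only if each test is run at 0.05 (0.076 exact, 0.107 one-sample Z). With Table 13 the error is 0.014, 0.031 or 0.062, according to the grade III-IV cut-off.

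These figures assume the 26%/74% split is true and covers every patient, the null rates are treated as known, and a stopped trial makes no efficacy claim. They also assume both rules count the same events. Table 13 counts events by day 100, whereas the grade III-IV success rule counts them over the whole study, so later cases could change the result slightly.

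**What to change.** 1. In 8.3.1 state one one-sided level (0.025), one test (exact binomial) and one cut-off: 8 or fewer of 60, actual alpha 0.014, power 85.8% at a 10% rate. Delete the conflicting p<0.05 and 7/36 statements. If the control rate is still to be updated, say beforehand that the cut-off will be recomputed by the same test at the same level.
2. Name one deciding GVHD test and reconcile it with the primary objective of grade II or greater.
3. Report grade II as an estimate with a confidence interval, not as stand-alone proof, because as defined it falls when severe GVHD rises.
4. If a second test is wanted, redefine it, for example as cumulative grade II-IV, and test it only after the first succeeds. Gating the present grade II test would be empty: 8 or fewer severe cases means 52 or more at grade II or lower, so it could never follow a grade III-IV success. A cumulative endpoint also needs a usable historical rate, since the stated split puts grade II-IV at 26% + 74% = 100%.

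**Cost.** Items 1 to 3 change wording only; item 4 would also need that historical rate. No efficacy claim can rest on grade II alone. Grade III-IV power is unchanged from the 0.025 tables but lower than the 0.05 exact figures: 58.8% falls to 44.4% at a 15% rate, and 82.2% to 71.0% at 12%.
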